The PEPNS System Feasibility Study is being conducted to confirm the feasibility of phrenic nerve stimulation in the neck with PEPNS System to pace the diaphragm. The study will be used to confirm:

- The benefits of ultrasound imaging in guiding the deployment of the pacing leads across the phrenic nerve in the patient's neck;
- The ease of lead deployment in the neck;
- The current stimulation levels required to stimulate and contraction of the diaphragm in synchrony with the ventilator's inspiratory breaths; and
- Stability of stimulation thresholds as patients are repositioned (supine, recumbent, lateral).

The PEPNS technology consists of two disposable multipolar stimulation leads and an external function generator designed to stimulate the phrenic nerve in synchrony with the inspiratory cycle of the ventilator. The purpose being to exercise the diaphragm during positive pressure ventilation to minimize the reduction in diaphragmatic strength.

Beyond testing the feasibility of the technology in humans the purpose of the study is to also:

- Demonstrate that the human experience is consistent with the preclinical trial results.
- Collect preliminary data that may refine the most suitable patient population for a pivotal study.
- Characterize diaphragm thickness observed on patients using mechanical ventilation and phrenic nerve electrical stimulation if feasible.

Diaphragm stimulation parameters in terms of currents, current profile waveforms, voltages and charge density are similar to those used in chronic diaphragm pacing patients where ventilatory support is replaced with pacing. Subjects will be treated per the standard of care for patients on ventilatory support, with weaning trials conducted up to 48 hours where weaning criteria are met. Time to weaning from mechanical ventilation will be collected. Adverse events will also be collected and analyzed.

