4.3.1 Frequency of Use

During this Feasibility Study, the PEPNS System is intended to be used for up to 2 days while the patient is on a mechanical ventilator in the ICU/CCU. During the study the PEPNS System will be used for up to 48 hours of continuous stimulation. The device is not intended for use outside of the hospital environment, such as a long-term care facility.

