6. STUDY DESIGN & METHODOLOGY

The study will examine performance and safety as defined in primary and secondary endpoints listed in Section 10. A maximum of up to 20 subjects will be enrolled in the study at up to 2 sites with up to 10 subjects per site. The final number of patients enrolled in the study will be based upon the time duration of the study and the rate of enrollment. In the first two patients, the investigator will stimulate the left phrenic nerve only and conduct CMAP tests and nerve conduction test on both phrenic nerves prior to and at least 3 weeks after the stimulation. These subjects will be examined 30 days' post study, to confirm safety of this method of stimulation of the phrenic nerve before enrolling the remaining patients up to a total of 20 subjects. After successfully demonstrating 30 day follow up on the initial two patients, stimulation will occur in both the left and right phrenic nerves simultaneously for the remainder of the trial. Typically, stimulation will occur once every 3 to 5 breaths and this decision will be left to the discretion of the attending physician. Figure 2 outlines the protocol for placement of the leads.

[figure not shown]

Figure 2. Study Left and Right Phrenic Nerve Pacing

Stimulation will occur for a maximum duration of 48 hours. A number of evaluations will also be conducted to measure the ease of placing and removing the stimulation leads as well as the ability of the lead to accommodate positional changes made by or to the patient.

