11.2 Index Procedure

Once the study subject or authorized representative signs an ICF and his/her eligibility to participate in the study is confirmed, the PEPNS System procedure can be initiated. A primary operator will be performing the PEPNS System procedure, but an additional qualified operator may be present or assisting. A Stimdia representative may also be present during index procedure to provide technical guidance to the primary operator.

The Investigator will follow the procedure technique outlined in LM0001, PEPNS System Operator's Manual.

Prior to the start of electrical stimulation, the subject's diaphragm thickness may be measured using ultrasound and the subject will have a 12 lead ECG. In addition, baseline standard blood gasses such as pH and paO_2 , paCO_2 , SaO_2 , HCO_3 etc. and exhaled gas analysis such as end-tidal CO_2 data will be garnered for up to 24 hours prior to stimulation.

A four pole pacing lead electrodes will be percutaneously placed beside the phrenic nerves using ultrasound guidance and the ultrasound screen shots will be captured if possible. The ease of gain pacing lead access and setup will be assessed and logged.

The subjects phrenic nerve(s) will then be electrically stimulated for up to 48 hours and device and procedure information, ventilation and PEPNS System stimulation will be recorded. In addition, patient vital signs including heart and respiratory rate, blood pressure, temperature, pH, paCO_2 , paO_2 , hematocrit, end-tidal CO_2 , will be collected when available unless otherwise specified in table 1 below. If the patient is weaned from the mechanical ventilator during this time the time to weaning will also be recorded. Also, a chest x-ray will be obtained if the patient has not had one in the last 30 days. In addition, Critical Care Pain Observation Tool^{22,23} (CPOT) and Richmond Agitation & Sedation Scale^{24,25} (RASS) assessments will be administered prior to the electrical stimulation and every 6 hours during it. Patients will also be physically observed for any muscle twitching during the simulation period to try and determine if any other nerves were stimulated. Diaphragm thickness may be measured again at 24 and 48 hours or at the end of the stimulation period.

The ability of the pacing lead to accommodate neck movement and patient positional changes will also be assessed and logged during electrical stimulation.

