11.3 Follow-Up Visits

All subjects will be followed up at 30 days to 37 days for adverse events and 30 ± 7 days for the chest x-ray. At this time hospital discharge and ventilation weaning time data will also be collected. Table 1 summarizes all required and optional test and procedures throughout the study including each visit's compliance windows.

Table 1: Study Procedures and Follow Up

Test / Evaluation	Screening (within 2 days pre-procedure)	Index procedure	30 day follow up
Signed Informed Consent	X		
Subject Demographics	X		
Medical History	X		
Height/Weight/BMI	X		
Blood Pressure	X		
Chest x-ray	X ¹		X
12 lead ECG		X	
Lead Insertion assessment		X	
1 hr. cessation of electrical stimulation		X	
Patient movement / repositioning assessment		X	
CMAP ²		X	X
CPOT/RASS assessments		X	
Muscle twitching observation		X	
Ultrasound screen shots (optional) Ventilation settings and end-tidal CO ₂ required Stimulation Data Vital Signs / pulse oximetry Standard Blood gases: pH, paO ₂ , PaCO ₂ etc. Diaphragm thickness (optional)		X	
Lead Removal assessment		X	
Adverse Events		X	X
Device Malfunctions		X	

¹ It is acceptable if this has been taken up to 30 days prior to the screening visit.

² Only for the first 2 patients enrolled.

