The percentage of patients who experience one or more serious device/procedure-related adverse events during the study will be reported. The evaluation results for the follow-up x-ray will also be noted.

Stim and Vent Synchrony

The phrenic nerve stimulation in synchrony with Mechanical Ventilation (MV) breaths will be measured to verify that it occurs with inspiration over all of the stimulated breaths for each of the patients. The synchrony on the detection of inspiration and expiration will be compared against the user set trigger flow section and compared to a fast trigger time which has been reported as 88 msecs.

Related Evaluations

Critical Care Pain Observation Tool (CPOT) assessments are made on all patients enrolled and will be reported before during and after stimulation on all patients. The pain assessment tool, CPOT, is based on four domains: the patient's facial expressions, body movements, compliance with ventilator (or voice use for non-intubated patients), and muscle tension. Each domain has a possible score of 0 to 2. The total score can vary between 0 and 8, where 0 indicates no pain behavior and 8 indicates clear signs of pain behavior.

Richmond Agitation and Sedation Scale (RASS) scores will be reported on all patients. The RASS measures agitation and sedation level, the score ranging from +4 to -5, where a score of 0 indicates an awake and adequate patient. Scores from -1 to -5 indicate an increasingly sedated patient, and scores from +1 to +4 indicate an increasingly irritable and agitated patient.

The CPOT and RASS scores will be evaluated to determine that the stimulation does not cause pain to the patient.

An assessment will be made to determine the sensitivity of the lead to patient position. Patient will be repositioned every 2 to 4hrs per hospital protocol and disease diagnosis requirements. Leads will be disconnected from the electrical stimulator using the extension lead during these non-stim periods. Reestablishing stimulation after reconnection will be evaluated along with the ability of the system to handle patient repositioning.

Vitals signs and blood gasses will be evaluated to determine if electrical stimulation does not have an untoward effect on patient. This will be evaluated by an expert in ICU ventilation / blood gas analysis.

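### Threshold stability under repositioning is a stated aim, but the SAP disconnects the leads for each scheduled move and defines no threshold or before/after measure, so re-established stimulation cannot stand in for it

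*SAP*

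**What the plan says.** The protocol raises the subject in four places.

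- Section 2 lists, among the things the study will confirm: "Stability of stimulation thresholds as patients are repositioned (supine, recumbent, lateral").
- Section 6 includes an evaluation of "the ability of the lead to accommodate positional changes made by or to the patient".
- Section 11.2 fixes the timing: "The ability of the pacing lead to accommodate neck movement and patient positional changes will also be assessed and logged during electrical stimulation".
- Table 1 in section 11.3 schedules a "Patient movement / repositioning assessment" at the index procedure, without saying what is measured.

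Section 4.3.1 adds: "During the study the PEPNS System will be used for up to 48 hours of continuous stimulation".

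The SAP takes it up in section 2 under Related Evaluations. It opens with "An assessment will be made to determine the sensitivity of the lead to patient position", continues with "Patient will be repositioned every 2 to 4hrs per hospital protocol and disease diagnosis requirements", and then says "Leads will be disconnected from the electrical stimulator using the extension lead during these non-stim periods". It will evaluate whether stimulation is regained after reconnection, together with how well the system copes with repositioning.

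Under Primary Endpoints, the SAP says that voltage follows from tissue impedance and a current set by the user, and that it is logged and checked against 10.5 volts. Section 11 of the SAP computes lag time and work of breathing for each stimulated breath.

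**The concern.** A threshold is the output needed to capture the nerve. To show that it is stable, one has to compare that output, or at least capture at a fixed output, before and after a change of position. The SAP names no such comparison. The one concrete item it evaluates, regaining stimulation, can succeed at a different current from the one used before the move. While the leads are disconnected, loss of capture during the move itself cannot be seen at all.

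The study is meant to confirm the procedures for a pivotal trial (protocol section 2), and SAP section 2 counts patient movement among the possible sources of mechanical damage. With no measure defined in advance, a favourable statement on positional stability would rest on judgement after the data are seen, and could be read as evidence about thresholds that was never assembled.

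**Working it through.** The plan gives no figure of its own on this point, so there is none to reproduce. The check is a comparison of the texts plus a short illustration.

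**1. Is stimulation running when movement is assessed?** Protocol section 11.2 places the assessment during stimulation, and section 4.3.1 calls the stimulation continuous. The SAP treats scheduled repositioning as a period without stimulation and with the leads disconnected. Read literally, these differ.

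**2. What is measured?**
- Sensitivity to position: no variable, comparison or criterion in either document.
- Regaining stimulation: no statement of the settings at which it counts as regained.
- Coping with repositioning: no definition.
- Threshold: not mentioned in the SAP paragraph.
- SAP Table 3: columns for lead preparation, placement, securement and removal, but none for repositioning.

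**3. What would regained stimulation show?** Because current is user set, regained capture fits two cases: same current and same capture, or changed current and same capture. Only the first is evidence of stability. Voltage is examined only against 10.5 volts, so a rise that stays below that limit passes. The documents do not say whether settings are re-adjusted at reconnection.

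**4. Would the primary capture rate reveal a problem?** It uses stimulated breaths only, so disconnected periods contribute nothing, and it is pooled over the whole period and judged against 80%.

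Inputs: 48 hours (protocol section 4.3.1) = 2,880 minutes; one move every 2 to 4 hours (SAP section 2); loss of capture after each move, *assumed*, since the documents give no value.

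- Moves per patient: 48/4 = 12 to 48/2 = 24.
- Share of time lost = minutes lost per move × moves / 2,880.

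| Assumed loss per move | 12 moves | 24 moves |
|---|---|---|
| 5 min | 60/2,880 = 2.1% | 120/2,880 = 4.2% |
| 10 min | 120/2,880 = 4.2% | 240/2,880 = 8.3% |
| 20 min | 240/2,880 = 8.3% | 480/2,880 = 16.7% |

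With full capture otherwise, the 10-minute case leaves a pooled rate of 91.7% to 95.8%. For the point estimate to fall to 80%, 0.20 × 2,880 = 576 minutes must be lost: 576/24 = 24 minutes after each of 24 moves, or 576/12 = 48 minutes after each of 12. If capture is instead restored at once by a change of current, the loss is zero and the capture rate carries no trace of the shift, provided voltage stays below 10.5 volts.

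The illustration uses time as a proxy for stimulated breaths. Its denominator includes disconnected time and the planned one-hour stop (protocol section 6.15). It concerns the point estimate; the test uses a lower confidence bound, which could miss 80% sooner.

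**5. How many moves could a paired analysis use?** 12 to 24 per patient, or 11 to 23 if none falls at hour 48. For the ten patients in SAP Table 3 that is 10 × 11 = 110 to 10 × 24 = 240, if all complete 48 hours. Protocol section 11.2 allows for earlier weaning, so the number may be smaller.

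**The case against.** A reader might infer that the SAP checks nothing except whether stimulation can be regained, and that instability therefore cannot show. The documents do not support either claim. The same SAP paragraph also names sensitivity to position and coping with repositioning, undefined as they are. Stimulation resumes in the new position; pressure, flow, work of breathing and stimulation are recorded at 1000 Hz (protocol section 4.2); and voltage is logged. A failed reconnection, lost capture or a voltage at or above 10.5 volts would leave a record, and the last two would score as non-capture. A reader might also infer that settings are routinely changed after each move. No passage says so.

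Further points have weight:

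- *During stimulation* in protocol section 11.2 can be read as during the stimulation period, which already contains a planned stop. Movements by the patient between scheduled moves would occur while connected. This softens the conflict but leaves it unresolved in the text.
- Repositioning is not among the specific objectives, the endpoints or the additional study data in protocol section 5, and no endpoint conclusion depends on it.
- The assessment log and the Operator's Manual are not among the documents reviewed and may hold more detail.
- Capture at unchanged settings is itself only a proxy: if stimulation is set above threshold, a modest shift can pass unnoticed.

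These points limit the weight of the concern. They do not supply a measure of threshold stability, and the protocol says that stability will be confirmed.

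**Conclusion.** The concern holds in a limited form. The protocol sets out to confirm threshold stability across positions. The SAP defines no threshold or before/after measure, cannot observe loss during a scheduled move, and has no planned analysis that would look for a shift in the data it does record. Regained stimulation is not evidence of an unchanged threshold.

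The size cannot be derived from the documents. Under the assumed 10-minute loss, about 4 to 8% of the time would be affected and the pooled capture rate would stay well above 80%; this shows how coarse that rate is and does not estimate what happened. It rests on the full 48 hours, the SAP's 2 to 4 hour interval and full capture otherwise.

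This is a worthwhile, inexpensive improvement to a descriptive evaluation. It does not threaten the primary or secondary endpoints.

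**What to change.** 1. Reconcile protocol sections 11.2 and 4.3.1 with the SAP's Related Evaluations on whether stimulation runs during repositioning. Which arrangement applies is a clinical matter, and this review takes no position on it.
2. In the SAP, replace regained stimulation as the stability measure with a paired summary for each move: current, voltage and breath-level capture immediately before disconnection and after reconnection, before any re-adjustment where such data exist.
3. Report the percentage of moves with capture kept at unchanged settings and the paired change in current and voltage, allowing for clustering by patient. Report moves that needed a settings change separately, as not shown to be stable.
4. Word the result as capture kept at unchanged settings, since that is what is observed.
5. Where move times, position or settings changes were not recorded, say so, limit the conclusion to stimulation re-established, and make no claim of threshold stability. This matters because the SAP already describes its ten-patient cohort, so new recording may not be possible.

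The cost is SAP wording and some work to align move times with the stimulation record. The stability figure may be less favourable than a statement that stimulation was regained.

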6.15 Additional Study Data

Time to weaning from mechanical ventilation data will be collected and reported.

The effect of electrical stimulation on diaphragm thickness, blood gas parameters, vital signs, end tidal CO₂ and tidal volume may be characterized. To this end, stimulation will be stopped for a single period of 1 hour within the middle period of the 6 hour blood gas analysis collection period, when the patient has been deemed to be hemodynamically stable by the attending physician. Data will be collected on blood gasses, pulse rate, blood pressure, SpO₂, end tidal CO₂ and tidal volume at the end of the 1 hour period. This data will be used to characterize the effect of electrical stimulation on hemodynamics. The mode of ventilation will also be recorded because stimulation is predicted to have little effect on tidal volume in flow controlled modes whereas it is predicted to increase in pressure control modes of ventilation. Tidal volume may also be adjusted to be the same as when electrical stimulation was turned on to eliminate any confounding effects of decreased minute and tidal volumes when stimulation is turned off. All other parameters such as breath rate, PEEP, FIO₂ etc. will be kept the same.

The diaphragm thickness may be measured prior to the stimulation, at 24 hours and at 48 hours or after the completion of all of the stimulation using ultrasound when clinically feasible, i.e., 0 hours, 24 hours and 48 hours or end of stimulation.

7. PROCEDURAL GUIDELINES (Treatment Procedure)

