2. ANALYSIS OBJECTIVES

The company informed the FDA of plans to conduct a First in Human feasibility study within an OUS Tier I country (Canada, Europe or Australia) and stated:

As part of this study the following would be evaluated

- a) Confirmation of the stimulation leads are easily deployed under ultrasound guidance
- b) Confirmation that the diaphragm is easily stimulated without collateral stimulation similar to the Taira publication in references.
- c) Confirmation of appropriate candidates for a pivotal study. Trending demonstrating that time to extubation is decreased when compared to historical data in similar patient population.

The first two patients enrolled in the trial will be analyzed specifically for safety of the procedure in terms of nerve damage which could result from electrical stimulation or mechanical damage due to lead insertion, patient movement or lead removal and any other adverse events. Compound motor action potential and nerve conduction time between the neck and diaphragm will be evaluated in the first two pilot patients. Since these patients are stimulated on the left phrenic nerve only, they will be included for the safety analysis only. The enrollment of subsequent patients was contingent upon these patients showing no damage to the phrenic nerve at ~30 days post stimulation in terms of the CMAP study, follow up x-ray and any reported adverse events deemed relevant to the procedure.

Primary and secondary endpoints for the study will be evaluated statistically in terms of per protocol (PP) and intent-to-treat (ITT) analysis. The clinical study protocol CIP0001 defined intent-to-treat as "All patients that were attempted to be treated with the PEPNS System but the procedure was aborted." The

	PEPNS Study Statistical Analysis Plan <small>CONFIDENTIAL: THIS DOCUMENT AND ALL INFORMATION CONTAINED HEREIN IS PROPRIETARY TO STIMDIA MEDICAL, INC. AND IS NOT TO BE DISCLOSED WITHOUT THE EXPRESS WRITTEN PERMISSION OF STIMDIA MEDICAL, INC.</small>	Document Number SAP0001	Rev. Level 1
---	--	-----------------------------------	------------------------

primary analysis will be per protocol and the secondary analysis will be intent-to-treat. Time of weaning from mechanical ventilation and diaphragm thickness from 0 to 48 hours will also be analyzed.

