6. STATISTICAL METHODOLOGY

STATISTICAL PROCEDURES

The primary statistical methods used in this study will be descriptive where continuous variable will be summarized using means, medians, standard deviation, minimums and maximums and categorical variables will be summarized using frequencies and percent for each categorical level.

The primary endpoint will be analyzed using a logistic regression where diaphragm capture (yes/no) is the dependent variable and time point and subject are the independent fixed effect and random effect predictors. The point estimate of the diaphragm capture rate will be estimated from logistic regression model along with a two-sided 95% confidence interval. The lower bound of that confidence interval will be compared to the performance goal of 80%. If the lower bound is above 80%, then the endpoint will have been achieved.

Secondary endpoints will be summarized as noted in the secondary endpoints section. Each endpoint will be summarized descriptively.

Additional evaluations will also be summarized descriptively. In addition, diaphragm thickness over time will be modeled using regression analysis. The slope parameter and 95% confidence intervals will be presented. Additional diaphragm thickness analyses may be run.

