If an interim analysis is performed, the database will be temporarily locked at the time of the interim analysis and the clinical study report will include the date that the data was transferred from the database to the statistician for the interim analysis. It will also specify whether or not the data had been monitored. The secondary end points and other remaining interim analyses will only be performed if the primary endpoints were met. If not, the study will continue to enroll patients and all study endpoints and additional analyses will be analyzed when enrollment has been completed. At the interim analysis the significance level used for testing will be 0.0125 which translates into calculating a 98.75% two-sided confidence interval on the capture rate and comparing the lower bound to 80%. At the final analysis (if needed) the significance level used for testing will be 0.0194 which translates into calculating a 98.06% two-sided confidence interval on the capture rate and comparing the lower bound to 80%. These levels were derived using a power cumulative error spending function with the parameter (rho) set to 1.0. This setting produces Pocock type boundaries (i.e. approximately equal spending for the two tests).

	PEPNS Study Statistical Analysis Plan <small>CONFIDENTIAL: THIS DOCUMENT AND ALL INFORMATION CONTAINED HEREIN IS PROPRIETARY TO STIMDIA MEDICAL, INC. AND IS NOT TO BE DISCLOSED WITHOUT THE EXPRESS WRITTEN PERMISSION OF STIMDIA MEDICAL, INC.</small>	Document Number SAP0001	Rev. Level 1
---	--	-----------------------------------	------------------------

7. MEASURES TO ADJUST FOR MULTIPLICITY, CONFOUNDERS, HETEROGENEITY, ETC.

Since the study cohort was 9 Caucasian men and 1 Caucasian woman and study was very small no heterogeneity, multiplicity or confounder statistical analyses will be run. However, summary data may be presented for the different types of patients (neuro trauma, COPD etc.) to try and see if there were any trends or if therapy was more effective for one of the patient populations since this was one of the study objectives.

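### Vital signs and blood gases are to be judged by expert review with no named contrast, estimate or interval; with 10 patients, seeing no effect cannot exclude an average shift of half an SD of the within-patient differences

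*SAP*

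**What the plan says.** SAP section 2, under Related Evaluations, states the aim: "Vitals signs and blood gasses will be evaluated to determine if electrical stimulation does not have an untoward effect on patient". The method is one sentence: "This will be evaluated by an expert in ICU ventilation / blood gas analysis". No variable, time point, comparator, estimate or interval is given.

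SAP section 6 plans descriptive summaries: "Additional evaluations will also be summarized descriptively". Apart from the capture analysis, the only interval it promises is for the slope of diaphragm thickness over time. SAP Table 3, although titled for patient vitals, has a column for screening blood pressure but none for on-stimulation vital signs or blood gases.

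Protocol 6.15 creates a within-patient comparison: "stimulation will be stopped for a single period of 1 hour within the middle period of the 6 hour blood gas analysis collection period". Blood gases, pulse rate, blood pressure, SpO2, end-tidal CO2 and tidal volume are collected at the end of that hour, and "This data will be used to characterize the effect of electrical stimulation on hemodynamics". The stop is a scheduled procedure in protocol Table 1. Protocol 11.2 also collects pre-stimulation blood gases and end-tidal CO2. The SAP mentions neither the stop nor a comparison with baseline for these variables.

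On numbers, SAP section 7 says "Since the study cohort was 9 Caucasian men and 1 Caucasian woman and study was very small", and Table 3 lists ten patient identifiers. Of the two left-side-only pilot patients, SAP section 2 says "they will be included for the safety analysis only". Protocol section 6 sets the ceiling: "A maximum of up to 20 subjects will be enrolled in the study".

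**The concern.** The question asked is whether an effect is absent. An expert reading individual records can recognise a gross event in one patient. That reading does not show how large an average change could be present and still go unseen. These are critically ill patients whose pressures and gases move for many reasons. Protocol 6.15 itself expects the effect on tidal volume to depend on ventilation mode and allows tidal volume to be adjusted during the stop.

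At stake is how one safety statement from a first-in-human study is worded and supported. Protocol 13.3 says the study will help define a pivotal trial. Without an estimate and interval, a reader of the report cannot tell a well-bounded null result from an uninformative one. Patients also undergo a planned interruption for which the SAP sets no analysis.

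**Working it through.** **There is no plan figure to reproduce.** The documents give no SD, effect size, limit or power for vital signs or blood gases. The check is how wide an interval the available patients could give.

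**Inputs from the documents.** n = 10 (SAP Table 3 and sections 7 and 8); n = 12 with the two pilot patients (SAP section 2); n = 20 (enrolment ceiling, protocol section 6).

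**Assumptions, not in the documents.** One paired difference per patient; differences roughly normal; two-sided 95% interval; shifts measured in SDs of the within-patient differences; half an SD as the illustrative shift.

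**Half-width of the 95% interval** = t(0.975, n−1) / √n, in SDs of the differences:

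| n | t(0.975, n−1) | √n | half-width |
|---|---|---|---|
| 10 | 2.262 | 3.162 | 0.72 |
| 12 | 2.201 | 3.464 | 0.64 |
| 20 | 2.093 | 4.472 | 0.47 |

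If the observed mean difference were exactly zero, the interval at n = 10 would run from −0.72 to +0.72 SD. A shift of 0.5 SD lies inside it, and also inside the interval at n = 12. At n = 20 it lies just outside.

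**Looking only at the harmful side.** A one-sided 95% bound at n = 10 lies t(0.95, 9)/√10 = 1.833/3.162 = 0.58 SD from the mean. An observed zero still does not exclude 0.5 SD.

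**Same question as power, for illustration only.** No test is planned. For a paired t-test at two-sided 0.05 and a true shift of 0.5 SD of the differences, noncentral-t power is 29% at n = 10, 35% at n = 12, 52% at n = 18 and 56% at n = 20. The shift would be missed 71%, 65%, 48% and 44% of the time.

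**If the SD is the between-patient SD.** With within-patient correlation r, SD of differences = between-patient SD × √(2(1−r)). At n = 10 the half-width in between-patient SDs is then 0.7154 × √(2(1−r)):

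- r = 0.5: 0.7154 × 1.000 = 0.72
- r = 0.8: 0.7154 × 0.632 = 0.45
- r = 0.9: 0.7154 × 0.447 = 0.32

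It equals 0.5 when 2(1−r) = (0.5/0.7154)² = 0.488, that is r ≈ 0.76. Above that correlation, a zero mean difference at n = 10 would exclude half a between-patient SD.

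**The case against.** The case for leaving the plan alone has real content.

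- **It is a descriptive item in a feasibility study.** Vital signs and gases are neither primary nor secondary endpoints. Protocol 6.9 plans no formal tests even for the secondary safety endpoints. This stands, and it is why no test or larger sample is asked for. It does not remove the need for an estimate when the aim is to judge absence of an effect.
- **Individual harm is captured elsewhere.** Adverse events include abnormal laboratory findings (protocol 13.4.1), and severity and relatedness are reviewed (13.5). This stands, and expert review of individual patients should stay. An average shift is a different question.
- **The SAP states no rule for declaring safety.** A reader might infer that stimulation will be declared harmless whenever the expert notices nothing. The wording does not support that: the aim is to determine whether there is an effect, and no rule for reaching the answer is given.
- **The pause data are not simply ignored.** A reader might infer that they go unused. Protocol 6.15 says they will be used to characterize the effect, and protocol 6.1 plans general summary statistics. What is missing is a SAP analysis of the contrast with an interval.
- **The pause contrast is imperfect.** It takes place only in patients judged haemodynamically stable, tidal volume may be adjusted, and the effect may depend on ventilation mode. This stands. It argues for showing those factors beside each difference, adding the baseline contrast, and not making the pause the sole gate for any safety statement.
- **More than one pair per patient may be usable.** Repeated readings could narrow the intervals, but the SAP plans no analysis of them for this purpose.

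**Conclusion.** The point holds as one about analysis and reporting. The SAP poses a yes/no question about untoward effects and leaves it to expert evaluation, with no contrast, estimate or interval, although the protocol schedules data that could supply them. At the SAP's cohort of 10, an observed mean difference of zero would leave shifts up to 0.72 SD of the within-patient differences unexcluded (0.64 at n = 12). A review that sees no effect therefore cannot exclude an average half-SD shift.

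This rests on one pair per patient, approximate normality, a 95% interval and the SD of the differences as the unit. Nothing in the documents says that half an SD is clinically relevant for any of these variables. A reader might infer that a half-SD shift would usually be missed whatever the circumstances. That goes too far: it does not hold at 18 to 20 patients, nor at n = 10 for a between-patient SD when within-patient correlation is 0.8 or higher (power 61% at 0.8 and 88% at 0.9). No primary or secondary endpoint is affected.

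**What to change.** Add to SAP section 2 (Related Evaluations), with a matching line in section 6:

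- For pulse rate, blood pressure, SpO2, blood gases and end-tidal CO2, tabulate for each patient (a) the last reading on stimulation minus the reading at the end of the 1-hour stop, and (b) the reading during stimulation minus the pre-stimulation baseline where available. State in advance which readings are paired.
- Show ventilation mode and any tidal-volume adjustment beside each difference.
- Summarise each difference as a mean with a 95% confidence interval. State whether the two pilot patients are included.
- Keep the expert review for individual patients.
- Word the conclusion as no untoward effect observed, with the interval giving the size of shift not excluded, rather than as a determination that there is no effect.
- If the sponsor wants to state that an effect is absent, its clinical expert should set the limit for that variable before seeing the paired data. The SAP already describes its cohort, so the report should record when any limit was set.

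The cost is a few SAP sentences and one table, largely from data the protocol already collects. The downside is a more cautious conclusion, since the intervals will be wide at this sample size.
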